Study Title:

**Efficacy of Tranexamic Acid in reducing requirement of blood transfusion
in Lower Limb Trauma Surgery: A prospective randomized controlled study**

Date: 05th July, 2021

Study Protocol

This study was a single-centre, randomized controlled parallel group study with 1:1 allocation. After obtaining ethical approval from IEC (**Ref No. PHMA/GSMCH-17/IEC-29A**), 116 patients of lower limb trauma presenting to Emergency Department of Civil Hospital, Rajpura between April 2017 to August 2018 were taken up for the study. Written informed consent was obtained from all the participating patients.

Patient selection

The patients, aged 18-60 years, suffering from lower limb trauma were taken up for the purpose of the study. The presence of old implant or infection at the fracture site, or any blood coagulation disorder were the exclusion criteria for the study. The patients undergoing percutaneous wire placement procedures for fracture fixation were also excluded from the study. The other exclusion criteria were polytrauma, non-consenting patients, psychiatric patient. 16 patients were excluded due to old fracture, percutaneous wire fixation or non-consenting patient. A total of 100 patients met the inclusion criteria and were enrolled.

Pre-operative evaluation

The enrolled patients were assessed preoperatively and all relevant investigations done. The patients were taken up for surgery after stabilization of the general condition. Pre-operative blood transfusion was done as required to have Hb level of at least 9.5mg/dl.

Surgical intervention

The patients were administered spinal anaesthesia or general anaesthesia, depending on the anaesthetist's discretion. The patients were treated by internal fixation of fracture by means of plates or interlocking nails. They were given antibiotic prophylaxis at the beginning of surgery. Intra-operatively, all the patients were given Ringer Lactate and intravenous colloid solution (Haemaccel) for volume replacement.

The patients enrolled were randomly divided into 2 groups. The random allocation of the patients to either group was done by one of the authors using a random number table. Group Tranexamic Acid (Group A) had 50 patients who were given 1 gram of TXA intravenously pre-operatively. IV TXA was administered, at the time of start of surgical incision, by mixing 1 g of TXA in 100 ml of normal saline. Control group (Group B) had 50 patients which were kept as a control group and were not given TXA.

Post-operative evaluation

The requirement of number of units of blood transfusion post-operatively was recorded as a primary outcome measure. The post-operative blood transfusion was done if the patients' Hb level fell below 9.5 mg/dl. The secondary outcome measures included change in Haemoglobin level, total length of hospital stay and the evidence of deep vein thrombosis by Wells score. Patients of both groups were monitored by checking Haemoglobin (Hb) level as required. The Hb readings were expressed as mean \pm Standard Deviation and range.

Other complications were monitored daily by looking for leg swelling for DVT, breathlessness and fall in saturation for pulmonary embolism, or a cardiac event

like angina or myocardial infarction, deterioration of mental status for stroke event. In case the patient would have any of these complaints, a medical opinion was sought and managed accordingly.

The probability of venous thromboembolism was suspected by use of Wells et al Clinical model to assess pre-test probability of DVT. Patients with a high probability were to be administered D-Dimer test and other relevant tests as needed to confirm thromboembolism.

No prophylactic treatment for DVT was planned. All the patients were monitored for development of DVT and treatment to be given for symptomatic cases only.

Renal function tests (RFTs) were done post surgery and at discharge. If the level of serum creatinine was elevated to above 1.4 mg/dl or the level of Blood Urea Nitrogen was higher than 25 mg/dl, then elevated RFT level was diagnosed and medical consultation was ordered.

Sample size calculation

Sample size was calculated based on a clinically significant effect with atleast 25% reduction in need of blood transfusion in the post-operative period. Assuming requirement of blood transfusion in control and intervention group to be 15% and 40% respectively, with a two-sided significance of 0.05 and a power of 80%, a total of 49 patients in each group would be required.

Statistical analysis

Statistical analysis was performed using Microsoft Excel 2016. Quantitative data comparison between groups was analyzed using two-sample student t-test. The level of significance was set at $p < 0.05$.

CONSORT

TRANSPARENT REPORTING of TRIALS

CONSORT 2010 Flow Diagram

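### Fracture site is used in neither allocation nor analysis, so the unadjusted comparison, though valid, may lose precision and be shifted by a chance site imbalance

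*Combined protocol and SAP*

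**What the plan says.** All references are to the combined protocol and SAP.

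- **Patient selection:** "The patients, aged 18-60 years, suffering from lower limb trauma were taken up for the purpose of the study". No bone or segment is named. The exclusions narrow the pool but do not single out a site. By type of procedure: "The patients undergoing percutaneous wire placement procedures for fracture fixation were also excluded from the study". By type of patient, the section adds further grounds, namely "The other exclusion criteria were polytrauma, non-consenting patients, psychiatric patient". Coagulation disorder, and infection or an old implant at the fracture site, are excluded as well.
- **Surgical intervention:** "The patients were treated by internal fixation of fracture by means of plates or interlocking nails". On allocation: "The random allocation of the patients to either group was done by one of the authors using a random number table". No strata or blocks are mentioned.
- **Enrolment:** "A total of 100 patients met the inclusion criteria and were enrolled", split 50 and 50.
- **Post-operative evaluation:** "The requirement of number of units of blood transfusion post-operatively was recorded as a primary outcome measure". Transfusion is triggered by haemoglobin falling below a threshold.
- **Sample size calculation:** one pair of transfusion rates, 15% and 40%, covers the whole mix.
- **Statistical analysis:** quantitative outcomes are compared by a two-sample t-test. No covariate or stratified analysis appears.

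**The concern.** The primary outcome follows blood loss through a haemoglobin trigger. Under this eligibility, a femoral nail and an ankle plate can sit in the same comparison. If those operations differ in transfusion need, two things follow.

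1. With 50 per arm and no stratification, one arm can by chance receive more of the high-bleeding fractures. The estimate from this one trial then moves for reasons unrelated to tranexamic acid. Without a site-by-arm table, a reader cannot see whether that happened.
2. Even with balanced arms, between-site variation stays in the error term of the t-test, so the estimate may be less precise than an adjusted one.

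**Working it through.** **Inputs from the documents.** 50 per arm; planned rates 40% and 15%; two-sided 0.05; power 80%. The sample size sentence attaches 15% to control and 40% to intervention. I take 40% as the control rate, since a reduction is planned; the sample size is the same either way.

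**The plan's own figure.** With the pooled-variance formula, n = [1.96 × √(2 × 0.275 × 0.725) + 0.842 × √(0.24 + 0.1275)]² / 0.25² = 48.9, so 49 per group. The stated figure reproduces and is not in dispute.

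**Assumptions, because the documents are silent.** There are two site groups. A share f of patients is in the high-bleeding group, and control risk differs by a spread s between groups. Overall rates stay at 40% and 15%, with a common risk ratio of 0.15/0.40 = 0.375. The outcome is transfused yes/no, a proxy for units, for which no SD is given.

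**Precision.**
- Unadjusted variance × n = 0.40 × 0.60 + 0.15 × 0.85 = 0.3675, so SE = √(0.3675/50) = 8.6 points.
- The spread is s in the control arm and 0.375s in the treated arm. The common site slope in an arm-plus-site linear model is their mean, b = 0.6875s.
- Share of variance removed: R = 2b²f(1−f)/0.3675. Effective n per arm = 50/(1−R), less about 1% for the extra parameter.

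| Spread s | Share f | Control risk, high / low | R | 50/(1−R) | After about 1% cost |
|---|---|---|---|---|---|
| 10 points | 0.5 | 45% / 35% | 0.006 | 50.3 | 50 |
| 20 points | 0.5 | 50% / 30% | 0.026 | 51.3 | 51 |
| 30 points | 0.5 | 55% / 25% | 0.058 | 53.1 | 53 |
| 50 points | 0.3 | 75% / 25% | 0.135 | 57.8 | 57 |
| 50 points | 0.5 | 65% / 15% | 0.161 | 59.6 | 59 |

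Simulation of the site-adjusted estimate agrees with the last column to within about one patient.

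**Imbalance.** With 50 femoral fractures among 100 patients and 50 per arm, the number in one arm is hypergeometric. Its SD is √(50 × 0.5 × 0.5 × 50/99) = 2.51, so the difference in share has SD 2 × 2.51/50 = 10 points. The probability of a difference of at least 12 points is 0.317, and of at least 20 points 0.071.

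**Shift in the estimate at a 50-point spread.**
- No treatment effect: imbalance × 0.50, so 0.12 gives 6 points and 0.20 gives 10 points. The SE with 40% in both arms is √(2 × 0.24/50) = 9.8 points.
- Planned effect: imbalance × 0.6875 × 0.50 = imbalance × 0.344, so 0.12 gives 4 points and 0.20 gives 7 points. The SE is 8.6 points.

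**Validity.** In simulation over spreads of 10 to 40 points, the unadjusted test kept type I error at 5.1-5.3%, and its mean estimate stayed at 25 points.

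**The case against.** The strongest reply is that broad eligibility is legitimate. The title sets lower limb trauma surgery as the target, the exclusions already narrow it, and an unstratified, unadjusted two-arm comparison is a valid analysis. This stands. A reader might infer that pooling the sites biases the result or inflates false positives. The documents do not support that: allocation is random, so site imbalance is random error that the ordinary SE already includes.

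A second reply is that the size rests on invented inputs. This also stands. Neither a site mix nor a rate by site is given, and at a 10-point spread the gain is nil. A reader might also credit adjustment with more than it delivers. Using control-arm variance alone, a 50-point spread with half femoral gives R² = 0.25 × 0.25/0.24 = 0.26 and 50/(1 − 0.26) = 68 per arm. That treats both arms as if they were at 40%. At the planned 15% in the treated arm site has less room to act, and the figure is about 59.

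A third reply is that the remedy comes late. Recruitment ran from April 2017 to August 2018, the document is dated July 2021, and the analysis is described in the past tense. Stratifying the list is no longer possible, and a covariate chosen now cannot be called pre-specified. This limits the remedy without removing it: fracture site is a baseline fact that treatment cannot alter. The documents do not say that site was recorded, so the remedy assumes that the operative record holds it.

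**Conclusion.** The point holds as a matter of efficiency and reporting. Fracture site plausibly predicts transfusion and is used nowhere. The unadjusted t-test remains valid, so no claim of bias or of a failed design follows. The gain from adjustment runs from nothing at a 10-point spread to the equivalent of 7-9 extra patients per arm at 50 points. A sizeable chance imbalance would move this trial's estimate by about one SE or less, even at that 50-point spread. All these sizes depend on the assumed site mix and spread, on a common risk ratio, and on a yes/no proxy for units transfused. The change is worth making because it costs little and loses almost nothing if site turns out not to matter.

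**What to change.** 1. Compare units transfused with a linear model containing arm and fracture site in two levels (femur v below the knee), taking site from the operative record.
2. Report this beside the unadjusted comparison, and state openly that the covariate was named after enrolment.
3. Tabulate fracture site and implant type by arm.

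The cost is one line in the Statistical analysis section, one item abstracted per patient, one degree of freedom, and a two-term regression, which Excel can fit. The drawback is that the covariate was not pre-specified, which is why both results should be shown. Stratifying the allocation list by site is advice for a future trial only.

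### DVT is a secondary outcome with no stated analysis beyond p < 0.05; at 50 per arm that criterion says little about a rare harm, and the plan asks for no confidence interval

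*Combined protocol and SAP*

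**What the plan says.** Under Post-operative evaluation, after naming units of blood transfused as the primary outcome, the plan states: "The secondary outcome measures included change in Haemoglobin level, total length of hospital stay and the evidence of deep vein thrombosis by Wells score". The same section describes further surveillance: "Other complications were monitored daily by looking for leg swelling for DVT, breathlessness and fall in saturation for pulmonary embolism, or a cardiac event", and goes on to angina, myocardial infarction and stroke. Those events are watched for but are not listed as outcomes.

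The Statistical analysis section gives one method, "Quantitative data comparison between groups was analyzed using two-sample student t-test", and one criterion, "The level of significance was set at" p < 0.05. It gives no test for a binary outcome, no confidence interval, and no rule for interpreting a harm outcome.

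Under Surgical intervention, each arm has 50 patients. The Sample size calculation section rests on transfusion alone. No DVT rate or precision target appears anywhere.

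**The concern.** A threshold on p answers one question: are the data surprising if the arms do not differ? For a rare harm in a small trial the answer will usually be no, whether or not the treatment causes harm. The useful question is how large an excess the data still allow, and only an interval answers it.

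The plan supplies a threshold and no interval, so a report that follows it can say of DVT only that the difference was or was not significant. The second statement is easily taken as reassurance about an antifibrinolytic drug. The plan also leaves the test for DVT open. For some plausible counts the choice of test decides which statement is made, and that choice could be made after the counts are known.

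**Working it through.** **Inputs from the documents.** 50 patients per arm (Surgical intervention); significance at p < 0.05 (Statistical analysis); transfusion rates of 15% and 40%, two-sided 0.05, 80% power, 49 per group (Sample size calculation).

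**Assumptions.** The documents give no DVT rate or count, so the counts and risks below are illustrative. DVT is treated as yes or no per patient. Tests are two-sided.

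**Step 1: the plan's own figure.** With mean rate 0.275,
n = [1.960 × √(2 × 0.275 × 0.725) + 0.8416 × √(0.15 × 0.85 + 0.40 × 0.60)]² / 0.25² = (1.238 + 0.510)² / 0.0625 = 48.9, so 49.
The stated size reproduces. It was set for a 25-point difference in transfusion, not for DVT.

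**Step 2: what p < 0.05 does with small counts.** For 3/50 v 0/50:
- Fisher: 2 × C(50,3)/C(100,3) = 2 × 19,600/161,700 = 0.242.
- Uncorrected chi-square: 100 × (3 × 50)² / (50 × 50 × 3 × 97) = 3.09, p = 0.079.

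The same methods, with the Yates correction and a t-test on 0/1 data added, give:

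| TXA v control | Fisher | Yates | Chi-square | t-test |
|---|---|---|---|---|
| 3 v 0 | 0.242 | 0.241 | 0.079 | 0.080 |
| 4 v 0 | 0.117 | 0.126 | 0.041 | 0.042 |
| 5 v 0 | 0.056 | 0.066 | 0.022 | 0.022 |
| 6 v 0 | 0.027 | 0.035 | 0.012 | 0.011 |

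3 v 0 is non-significant by all four, and 6 v 0 is significant by all four. Between them the result depends on the test. With 0 v 0 the pooled variance is zero, so the t statistic is 0/0 and there is no result.

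**Step 3: what the intervals show.** The Newcombe interval combines the Wilson limits (l, u) of each arm:
lower = d - √[(p1 - l1)² + (u2 - p2)²], upper = d + √[(u1 - p1)² + (p2 - l2)²], where d = p1 - p2.
- 0/50: Wilson upper limit = 1.96²/(50 + 1.96²) = 3.84/53.84 = 7.1%. So 0 v 0 gives -7.1 to +7.1 points.
- 3 v 0: Wilson limits for 3/50 are 2.1% and 16.2%. Lower = 6.0 - √(3.94² + 7.13²) = -2.1; upper = 6.0 + 10.2 = +16.2 points.
- 2 v 1: -7.0 to +11.6 points.
- 5 v 0: +0.9 to +21.4 points.

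Within one arm, 0/50 has an exact two-sided 95% upper limit of 1 - 0.025^(1/50) = 7.1%.

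**Step 4: power at 50 per arm.** Sum the product of the two binomial probabilities over every pair of counts with p < 0.05.

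| Assumed risk, control to TXA | Fisher | Chi-square |
|---|---|---|
| 2% to 8% | 9% | 26% |
| 5% to 10% | 6% | 14% |
| 2% to 10% | 19% | 38% |

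**The case against.** **The 5 v 0 example.** A reader might say that even 5 DVTs against none would be declared non-significant. That is true only with Fisher (0.056) or Yates (0.066), and the plan specifies neither. By the t-test, the only test it names, and by plain chi-square, p is 0.022. The Newcombe interval for 5 v 0 also excludes zero. The example that holds whichever of the four tests is used is 3 v 0.

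**No rule for DVT at all.** The threshold follows directly on a sentence about quantitative data, so it can be argued that the plan sets no criterion for DVT. That is fair, but it leaves a gap where a method should be, and p < 0.05 remains the only criterion on offer.

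**A hazard would be reported as safety.** A reader might infer this. The documents contain no safety hypothesis, no non-inferiority margin, and no statement that non-significance will be taken as safety. The risk is of misreading, not of a planned conclusion.

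**An excess of 7 points could never be excluded.** This depends on the counts. With 0 on TXA and 1 on control, the Newcombe upper limit is 5.3 points.

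**Most thrombotic events are left out.** The documents give no event rates, so nothing shows that embolism, cardiac events and stroke would outnumber DVT. They do show that these events are monitored and are not listed outcomes.

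**Low power for harms is ordinary.** Trials sized on efficacy usually have little power for rare harms, and that alone is no fault. It is, however, the reason to report an interval rather than a test result.

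**Conclusion.** The concern holds as a gap in analysis and reporting. DVT is a named outcome with no binary method, no interval, and a threshold that says little at 50 per arm. A split of 3 v 0 would be non-significant by all four tests while the data allowed an excess of up to 16 points. No events in either arm would still allow a difference of up to 7.1 points in either direction. An assumed fourfold rise from 2% to 8% would be missed about three times in four by the more sensitive tests (26% power) and about nine times in ten by Fisher (9%).

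The intervals follow from the arm size and the illustrative counts. The power figures rest on assumed risks, because the documents give none. The primary outcome is unaffected, and nothing here shows that TXA raises or does not raise thrombotic risk.

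**What to change.** In the Statistical analysis section:

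- State that DVT is not judged by p < 0.05.
- Report the number of patients with DVT in each arm with an exact (Clopper-Pearson) 95% interval, and the risk difference with a Newcombe 95% interval. Say whether a DVT means a high Wells score or a confirmed event.
- Quote the upper limit of the risk difference in the conclusion. Make no statement that TXA does not increase thrombosis on the basis of p > 0.05.
- Report the pulmonary embolism, cardiac and stroke events already monitored, by arm, in the same way.
- A combined thrombotic outcome is optional. The plan describes signs to watch for rather than event definitions, and the document is dated July 2021, after the stated inclusion period ended in August 2018. Any composite would need definitions and should be labelled post hoc.

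No new patients, visits or measurements are needed. The main cost is a weaker safety conclusion than a statement of no significant difference. A composite, if added, would also need case review.

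### Total hospital stay, read plainly, includes pre-operative days that TXA cannot affect; with an unadjusted t-test this costs precision, without bias, on a secondary outcome

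*Combined protocol and SAP*

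**What the plan says.** Under Post-operative evaluation the plan states: "The secondary outcome measures included change in Haemoglobin level, total length of hospital stay and the evidence of deep vein thrombosis by Wells score". This is its only mention of "total length of hospital stay", and it gives no start or end point.

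Three other places bear on what total stay contains:

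- **Study Protocol:** enrolment drew on "116 patients of lower limb trauma presenting to Emergency Department", so patients entered through an emergency route.
- **Pre-operative evaluation:** "The patients were taken up for surgery after stabilization of the general condition". The same paragraph adds: "Pre-operative blood transfusion was done as required to have Hb level of at least 9.5mg/dl".
- **Surgical intervention:** "IV TXA was administered, at the time of start of surgical incision".

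Under Statistical analysis the method is: "Quantitative data comparison between groups was analyzed using two-sample student t-test". No covariate or other adjustment is described, and no stay counted from surgery is mentioned.

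**The concern.** Total stay is the sum of a wait before surgery and a recovery after it. Only the recovery can respond to a drug given at incision. The wait depends on how long each patient takes to be investigated, stabilised and, where needed, transfused, so it is likely to vary between patients for reasons unrelated to treatment. An unadjusted t-test leaves that variation in its standard error.

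The expected difference between arms is the same whether stay is counted from admission or from surgery. Unless longer waits go with clearly shorter recoveries, total stay estimates that difference with a wider confidence interval. What is at stake is the chance of detecting a real effect on recovery time. The primary outcome is already confined to the period after surgery, and this secondary outcome is not.

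**Working it through.** **The plan's own figure.** The only sample size in the plan concerns the proportion transfused. The inputs, from Sample size calculation, are rates of 15% and 40%, two-sided 0.05 and 80% power. With pooled variance and mean rate 0.275:

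n = [1.960 × √(2 × 0.275 × 0.725) + 0.842 × √(0.40 × 0.60 + 0.15 × 0.85)]² / 0.25² = (1.238 + 0.510)² / 0.0625 ≈ 48.9, rounded up to 49.

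The stated 49 per group is reproduced. It says nothing about length of stay, for which the plan gives no SD, expected difference or power.

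**Inputs for length of stay.** From the documents: 50 patients per arm, and an unadjusted two-sample t-test. The significance level is 0.05, taken as two-sided. Assumed, because the documents are silent:

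- r = SD of pre-operative stay / SD of post-operative stay;
- ρ = correlation between the two;
- a true effect that post-operative stay would detect with 80% power.

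**Formulas** (normal approximation, in units of the post-operative SD):

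- Detectable effect on post-operative stay: (1.960 + 0.842) × √(2/50) = 2.802 × 0.2 = 0.56 SD.
- Variance of total stay: V = 1 + r² + 2ρr.
- Power on total stay for the same effect: Φ(2.802/√V − 1.960).
- Number per arm that restores 80% power: 50 × V, rounded up.

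**Results with ρ = 0:**

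| r | V | Power on total stay | n per arm for 80% |
|---|---|---|---|
| 0.25 | 1.0625 | 77.6% | 54 |
| 0.5 | 1.25 | 70.7% | 63 |
| 1 | 2.00 | 50.8% | 100 |
| 1.5 | 3.25 | 34.2% | 163 |

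**Sensitivity to correlation:**

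| r | ρ = −0.3 | ρ = 0 | ρ = +0.3 |
|---|---|---|---|
| 0.25 | 83.5% | 77.6% | 72.0% |
| 0.5 | 82.0% | 70.7% | 61.4% |
| 1 | 65.8% | 50.8% | 41.2% |
| 1.5 | 44.7% | 34.2% | 27.9% |

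Total stay is the more precise measure only when V < 1, that is r² + 2ρr < 0, or ρ < −r/2. At r = 0.5 this needs ρ below −0.25; at r = 1, below −0.5.

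**Adjustment.** If total stay is regressed on arm and pre-operative days, and the relation is linear, the residual variance is 1 − ρ², which is never above 1. For r = 0.5 and ρ = −0.3 it is 1 − 0.09 = 0.91, against 0.95 for unadjusted total stay and 1 for post-operative stay. Apart from the one degree of freedom it uses, adjustment therefore does at least as well as either unadjusted measure, whatever the sign of ρ.

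**The case against.** The strongest reply is that the size of the loss is wholly assumed. The plan gives no waiting times and no SD. It limits age to 18–60 and excludes polytrauma, which may narrow the spread of waits. At r = 0.25 the loss is about two percentage points, and with a modest negative correlation total stay can come out slightly ahead. This stands. A reader might infer a substantial, established loss of power, but the documents support only a loss that ranges from negligible to large with r and ρ. They do not suggest the negative correlation that would reverse it.

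A reader might also infer that unequal waits could bias the comparison or produce false positives. They do not support that. Randomisation balances waits on average, and their variance is already in the t-test's standard error. At 50 per arm the chance difference in mean wait has a standard error of √(2/50) = 0.2 pre-operative SDs, and the test allows for it. Type I error stays at its nominal level.

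A third reply is that total stay is a legitimate measure of hospital burden, and the plan does not say which purpose it had in mind. That is a reason to keep reporting it. It is not a reason to leave the comparison imprecise, because any effect of TXA on burden also arises after incision.

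Finally, a reader might conclude that total stay should be replaced. Recruitment ran from April 2017 to August 2018, the document is dated 5 July 2021, and the analysis is described in the past tense. Demoting a named outcome at that stage would be a post hoc change. This objection also stands, and it shapes the fix.

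**Conclusion.** The point holds as one of precision. On its plain reading the outcome includes days that treatment cannot influence, and the planned test does nothing to remove their variance. With uncorrelated components, 80% power on post-operative stay becomes about 78%, 71%, 51% or 34% on total stay as the SD ratio goes from 0.25 to 0.5, 1 and 1.5. These figures illustrate a range and do not estimate the loss in this trial.

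The conclusion rests on three assumptions: total stay starts before surgery, waits vary between patients, and ρ is not below −r/2. The missing definition of start and end is a gap in its own right, whatever the size of the loss. The importance is minor: the outcome is secondary, no power was claimed for it, and the primary result and its sample size are unaffected.

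**What to change.** 1. State when stay starts and when it ends.
2. Add a between-arm comparison of post-operative stay, from day of surgery to discharge, or analyse total stay with pre-operative days as a covariate. The first can use the t-test already planned; the second needs a regression.
3. Keep total stay reported as specified. If stay has already been compared between arms, label the added analysis as post hoc.
4. Report the mean and SD of pre-operative stay by arm, so that readers can see how much the wait contributed.

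The cost is one extra analysis and one subtraction per patient. It needs the date of surgery. The documents do not say that this was collected, so it would have to come from the hospital record.

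### The primary outcome depends on a low Hb being found, yet Hb checks have no common schedule and no masking is described; the readings behind Hb change are also undefined

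*Combined protocol and SAP*

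**What the plan says.** The Post-operative evaluation section names the primary outcome: "The requirement of number of units of blood transfusion post-operatively was recorded as a primary outcome measure". Transfusion follows when the "Hb level fell below 9.5 mg/dl". The only rule for measuring Hb is "Patients of both groups were monitored by checking Haemoglobin (Hb) level as required", which gives no times, minimum frequency or criteria for testing.

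Other monitoring in the same section is more definite. For renal tests: "Renal function tests (RFTs) were done post surgery and at discharge". For clinical events: "Other complications were monitored daily by looking for leg swelling for DVT", with similar daily review for pulmonary embolism, cardiac events and stroke. Hb is not on that daily list.

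Under Surgical intervention, the TXA group receives an infusion and the control group receives none. One of the authors made the allocation. The document mentions neither a placebo nor masking of patients, ward staff or assessors.

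On Hb as an outcome: "The secondary outcome measures included change in Haemoglobin level, total length of hospital stay and the evidence of deep vein thrombosis by Wells score". The Pre-operative evaluation section adds "Pre-operative blood transfusion was done as required to have Hb level of at least 9.5mg/dl". The Statistical analysis section gives one method: "Quantitative data comparison between groups was analyzed using two-sample student t-test".

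**The concern.** A transfusion that depends on a threshold can happen only if someone measures the value. The numeric trigger limits discretion once Hb is known; it does not govern whether or when Hb is checked. If staff know the arm and check one group less, some low values in that group may never be found, and those patients count as zero units. Fewer checks in the TXA arm could create an apparent effect, and fewer in the control arm could hide a real one. If sparse checking only delays detection and the same units are given, the primary outcome is not distorted. Without the number and timing of checks by arm, a reader cannot tell these cases apart.

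The lesser point concerns Hb change. The plan does not say whether the first reading comes before or after any pre-operative transfusion, or whether the second comes before or after any post-operative one. Both kinds of transfusion raise Hb. If controls receive more blood after surgery, a post-transfusion reading would understate their fall.

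**Working it through.** **The plan's own figure.** The Sample size calculation section uses 15% and 40%, two-sided 0.05 and 80% power:

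n = [1.960 × √(2 × 0.275 × 0.725) + 0.842 × √(0.15 × 0.85 + 0.40 × 0.60)]² / 0.25² = 48.9, so 49 per group, as stated. No figure in the plan is disputed here.

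**How large could the distortion be?** The documents give no testing rates, so this is an illustration only.

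From the plan: 50 per arm, two-sample t-test on units, 0.05 two-sided, and rates of 40% and 15%. I give 40% to control and 15% to TXA; the plan prints them in the other order.

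Assumed:
- Transfused patients receive 1, 2 or 3 units with probabilities 60/30/10%.
- A fraction d of the low Hb values in one arm is found, and all are found in the other arm.
- A missed patient counts as 0 units.
- Misses are either random, or fall only on patients who would have had 1 unit. In the second case the miss probability among those patients is (1 − d)/0.6.

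Mean units per transfused patient: 0.6 × 1 + 0.3 × 2 + 0.1 × 3 = 1.5. The assumed effect is therefore 0.40 × 1.5 − 0.15 × 1.5 = 0.60 − 0.225 = 0.375 units.

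Shift in an arm where 40% are truly below the trigger:
- random misses: 0.60 × (1 − d) = 0.06, 0.12, 0.15 at d = 90, 80, 75%;
- 1-unit misses only: 0.40 × (1 − d) = 0.04, 0.08, 0.10.

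As a share of 0.375, these are 16, 32 and 40% for random misses, and 11, 21 and 27% for 1-unit misses only.

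The tables below come from 400,000 simulated trials per setting with a pooled-variance t-test.

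(a) False-positive rate: no true effect, 40% below the trigger in both arms, all found in control.

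| Found in TXA arm | Random misses | 1-unit misses only |
|---|---|---|
| 100% | 5.0% | 5.0% |
| 95% | 5.3% | 5.2% |
| 90% | 6.6% | 5.6% |
| 80% | 11.4% | 7.7% |
| 75% | 15.1% | 9.2% |

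If checks are only delayed and the same units are given, the rate stays at 5.0%.

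(b) Power: control 40% and TXA 15% truly below the trigger, all found in TXA.

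| Found in control arm | Random misses | 1-unit misses only |
|---|---|---|
| 100% | 72.3% | 72.3% |
| 90% | 59.2% | 62.5% |
| 80% | 44.4% | 51.8% |
| 75% | 37.1% | 46.4% |

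(c) Equal misses, 80% found in both arms: the false-positive rate stays at 5.0% and power is 60.2% (random) or 60.8% (1-unit only). Equal under-detection costs power but does not create a false effect.

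**Cross-check on proportions.** I applied a two-proportion z-test to the share transfused, with no true effect and 40% below the trigger. With 90% found in the TXA arm the apparent difference is 0.40 − 0.36 = 4 points and the chance of a significant result is 6.9%. With 80% found, the difference is 8 points and the chance is 13.2%. The picture is similar.

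**Hb change.** No arithmetic applies. The pre-operative section allows transfusion before surgery and the post-operative section allows it afterwards. Neither section, nor the list of secondary outcomes, ties the two readings to those transfusions.

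**The case against.** The route to bias needs three links: post-operative staff who know the arm, that knowledge changing how often they check Hb, and low values that are never found rather than found later. The document shows none of them. It does not say who ordered Hb tests, and the absence of masking is inferred from silence. This stands, and it is why the point is a risk and not a finding of bias.

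There is also partial protection. One monitoring rule covers both groups, the trigger is numeric, and daily clinical review makes a large unnoticed fall less likely. Hb change is an outcome and Hb readings are summarised, which suggests at least one post-operative reading per patient. That also has weight, but it sets no common schedule and does not exclude a later fall going unfound. Shared discretion, used by staff who may know the arm, does not guarantee equal testing.

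The size rests wholly on assumptions. The larger false-positive rates need 20-25% of low values to be permanently missed in one arm only. That is correct. In (b), the starting power of 72% reflects a t-test on assumed unit counts in a trial sized on proportions. That is a separate matter; only the fall from 72% bears on this point.

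Finally, the document is dated July 2021 and describes, in the past tense, patients taken up from April 2017 to August 2018. A draw schedule cannot be imposed on them. This stands: for those patients the remedy is disclosure.

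**Conclusion.** The concern holds and should be acted on, with medium confidence. Detection of the event that generates the primary outcome is left to unscheduled testing, in a trial that describes no masking. The documents do not show that testing differed between arms.

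The size depends on the gap in detection. At 90-95% found in one arm the false-positive rate is 5.2-6.6%, which is minor. At 75-80% it is about 8-15%, or power falls from 72% to 37-52% if the gap runs the other way. These figures rest on the assumed detection rates, direction and units per patient, and on missed patients receiving no units.

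The undefined readings for Hb change are a real but lesser gap, affecting a secondary outcome.

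**What to change.** **Hb checks.** For any patients still to be treated, replace the as-needed wording with a common minimum set of post-operative Hb draws, identical in both arms and chosen by the investigators. Keep extra checks when clinically needed, and report the number of checks per patient by arm. For patients already treated, report the number and timing of Hb checks by arm from records, and state that no masking was used if that is so.

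**Hb change.** Define it as the last Hb before incision, after any pre-operative transfusion, minus the Hb at one fixed early post-operative draw. For patients already treated, use the first recorded post-operative Hb, give its timing by arm, and report how many patients per arm were transfused before it.

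**Cost.** For further patients: a few routine Hb tests each and two sentences of wording. For those already treated: a record review of check counts, check times and transfusion times. Extra checks remain possible and the first recorded Hb may differ in timing between arms, so the route to bias is narrowed and made visible, not closed. No dose, trigger or treatment rule changes.
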